6.1 Intention-To-Treat population (ITT)

The ITT population includes all subjects who:

- Are randomised, and
- Receive at least one dose of study medication, and
- Provide a Baseline and at least one post-Baseline FEV1 value.

Patients will be included in the analysis per the treatment to which they were randomised.

Note: the 'Baseline' FEV1 value refers to the last non-missing FEV1 value assessed prior to the first dose of study medication.

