7.1.4.10 Time to next COPD exacerbation

The time to next COPD exacerbation (in days) is defined as:

(Date when first COPD exacerbation symptoms started – Date when current COPD exacerbation symptoms stopped),

where COPD exacerbations experienced during the study are recorded on the ‘Acute Exacerbation COPD’ form of the eCRF, i.e.:

- Start date of COPD exacerbation is the ‘date when symptoms started’ recorded on the form
- COPD exacerbation has an intensity recorded as ‘Mild’, ‘Moderate’ or ‘Severe’ on the form.

Table 4: Criteria for event/censored for assessment of Time to next COPD exacerbation

Situation	Date of event or Censoring	Time to next COPD exacerbation	Outcome
Subjects who had next COPD exacerbation	Date of next COPD exacerbation after entering in study	Time from when current COPD exacerbation symptoms stopped until Date of next COPD exacerbation after entering in study	Event
Subjects who never had COPD exacerbation in study period	Withdrawal or last contact date	Time from when current COPD exacerbation symptoms stopped until Date of withdrawal or last contact date	Censored
Subjects who died	Death date	Time from when current COPD exacerbation symptoms stopped until Date of death	Censored
Subjects who withdrew or were lost to follow-up during the study	Withdrawal or last contact date	Time from when current COPD exacerbation symptoms stopped until Date of withdrawal or last contact date	Censored

7.1.4.11 Time from hospitalisation admission until subject is medically ready for discharge (current COPD)

This time (in days) will be calculated as:

(Date subject is medically ready for discharge from hospital – Date of hospitalisation admission),

where ‘Date of hospitalisation admission’ and ‘Date subject is medically ready for discharge from hospital’ are recorded on the ‘Current COPD Exacerbation’ form of the eCRF.

Table 5: Criteria for event/censored for assessment of Time from hospitalisation admission until subject is medically ready for discharge (current COPD)

Situation	Date of event or Censoring	Time from hospitalisation admission until subject is medically ready for discharge	Outcome
Subjects who were medically ready for discharge from hospital	Date subject is medically ready for discharge	Time from hospitalisation admission until Time subject is medically ready for discharge	Event

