8.1.5 Definitions of Baseline

The efficacy/exploratory endpoints to be analysed separately during the Acute Exacerbation Phase and the Stabilisation Phase are the EXACT-PRO total score and subscores (and exacerbation parameters derived from EXACT-PRO), the change from baseline in CRQ over time and the change from baseline in mMRC dyspnoea scale over time.

For summary purposes, the baseline value for Acute Exacerbation Phase will be defined as the last non-missing value collected prior to the first dose of study medication, unless other specified. Moreover, for the efficacy/exploratory endpoints to be analysed separately during the Acute Exacerbation Phase (from Study Day 1 until Day 14) and the Stabilisation Phase (from Day 14 until Week 26), the baseline value for Stabilisation Phase will be defined as the value collected on Visit 9 (Day 14), unless other specified. For Stabilisation Phase, no value available prior to Visit 9 (Day 14) will be used for definition of baseline, as the patient might not yet be under stable condition for COPD prior to Day 14.

For EXACT-PRO, as there is no stable period during which EXACT-PRO scores are collected prior to administering the study drug, the definition of the Baseline EXACT-PRO from the user manual⁶ will not be used for Acute Exacerbation Phase. The score and subscores obtained on Day 1 of the EXACT-PRO observation period, which corresponds to Study Day 1, will be used as the baseline for Acute Exacerbation Phase. Moreover, the Baseline EXACT-PRO score (or subscores) for Stabilisation Phase will be defined as the mean EXACT score during the first 7 days of the Stabilisation Phase (Week 3; Days 15-21), with a minimum of 4 days of available data required to compute the baseline value. If 4 or more of the first 7 days of data are not available, the baseline EXACT-PRO score for Stabilisation Phase will not be calculated.

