8.6.3 Analysis of secondary efficacy endpoint(s)

The analysis of secondary efficacy endpoints will be performed on the ITT and PP populations.

8.6.3.1 Comparison of FEV1 on Days 3, 10, and 14

A descriptive summary table will be presented for FEV1 absolute values and change for baseline on Days 3, 10, and 14 by treatment regimen and visit.

Change in FEV1 from baseline (pre-dose) to Day 3 will be analysed using an ANCOVA model estimating the effect at Day 3, using OC, including treatment, severity of airflow limitation at baseline, blood eosinophils (%) value at baseline, time from start of current COPD exacerbation to first IMP dosing, presence of cardiovascular comorbidities at screening and COPD exacerbation treatment at screening as fixed effects and baseline FEV1 value as a covariate.

The ANCOVA model results will be presented with LSMEAN and standard error (SE) of each treatment regimen as well as the adjusted mean difference between treatment regimens at Day 3 and associated two-sided 95% CIs. Each pairwise treatment regimen comparison will be tested at an alpha level of 5%. P-values of the effects will also be presented.

A similar ANCOVA model will be used for analysis of:

- Change in FEV1 from baseline to Day 10
- Change in FEV1 from baseline to Day 14.

Additionally, similar analyses as detailed above (descriptive summary table and ANCOVA model) will be performed for:

- Comparison of FVC on Days 3, 7, 10, and 14 (Note: ANCOVA model includes baseline FVC value as a covariate)
- Comparison of FEV1/FVC on Days 3, 7, 10, and 14 (Note: ANCOVA model includes baseline FEV1/FVC value as a covariate).

Furthermore, descriptive summary tables will be presented for the following spirometry parameters (i.e. absolute values and change for baseline on Days 3, 7, 10, and 14 by treatment regimen and visit):

- FEV1 % of predicted normal value
- FVC % of predicted normal value
- FEV1/FVC % of predicted normal value.

8.6.3.2 Normalisation of spirometry parameters over time compared with the most recent test performed within the last 12 months outside an exacerbation

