8.6.3.13.2 Time to next COPD exacerbation based on EXACT-PRO total score

COPD-related exacerbations during the Stabilisation Phase based on EXACT-PRO total score will be considered for this analysis.

Appendix C describes the EXACT raw scores and EXACT scoring instructions to compute the EXACT daily scores and event frequency, duration and severity.

Time to next COPD exacerbation during the Stabilisation Phase will be analysed using the Kaplan-Meier method. Patients without a COPD exacerbation or who are discontinued before having it will be considered as “censored” patients.

For the following study periods in the Stabilisation phase: [2-6) weeks, [6-10) weeks, [10-14) weeks, [14-18) weeks, [18-22) weeks and [22-26) weeks, the number of COPD exacerbation-free patients at the beginning of the period, the cumulative number of patients with COPD exacerbation at the end of the period and the probability of having experienced a COPD exacerbation at the end of the period with the associate two-sided 95% CIs will be presented by treatment regimen. The point estimates and the relative two-sided 95% CIs will be presented by treatment regimen for the 75th, 50th and 25th percentiles. A Kaplan-Meier plot will also be presented. Comparisons between treatment regimens will be performed by means of the log-rank test. The p-values of the pairwise log-rank test comparisons will be displayed on the figure.

8.6.3.14 Time from hospitalisation admission until the subject is medically ready for discharge (current COPD)

Time from hospitalisation admission until the subject is medically ready for discharge (current COPD) will be analysed using the Kaplan-Meier method. Only patients with initial hospitalisation for COPD date on or prior to Study Day 1 (i.e. in hospital on Day 1) are included in this analysis. Patients who are discontinued before being medically ready for discharge will be considered as “censored” patients.

For the following study periods: [0-1) days, [1-2) days, [2-3) days, [3-4) days, [4-5) days, [5-6) days, [6-7) days, [7-8) days, [8-9) days, [9-10) days, [10-11) days, [11-12) days, [12-13) days, [13-14) days and [14 days-End of Study], the number of patients not medically ready for discharge at the beginning of the period, the cumulative number of patients medically ready for discharge at the

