Two parameters are required to identify event frequency: (1) Baseline and (2) Onset. Baseline has been previously described for Acute Exacerbation Phase and for Stabilisation Phase. Due to the design of the study, the EXACT-PRO user manual definition of “Onset” will not be used for Acute Exacerbation Phase, and the EXACT-PRO value on Study Day 1 will replace the “Onset” in the definitions. Therefore, event frequency will not be identified for Acute exacerbation Phase.

Nevertheless, the EXACT-PRO user manual definition of “Onset” will be used for Stabilisation Phase. Onset is defined as the first day in which the patient experiences an acute, sustained worsening of their baseline condition. Therefore, event frequency will be identified for Stabilisation Phase.

Onset

Onset is identified in 1 of 2 ways: *Either* (1) an increase in EXACT score ≥ 12 points above the patient’s mean Baseline for 2 consecutive days, with Day 1 of the 2 days serving as Day₁ (Onset) of the event **OR** (2) an increase ≥ 9 points above the patient’s mean Baseline for 3 consecutive days, with Day 1 of the 3 days serving as Day₁ (Onset) of the event. The presence of either constitutes Onset of an event during the Stabilisation Phase. Note that the requirement of consecutive days is the reason the data file must have a record for every day for a patient, even if the EXACT score is missing.

Event Duration (Stabilisation Phase)

Event Duration requires identification of the following parameters: (1) Onset; (2) 3-day Rolling Average; (3) Maximum Observed Value; (4) Threshold for Improvement; and (5) Recovery. It is possible that Improvement may occur at multiple timepoints during an event and that this Improvement may or may not reflect full Recovery. As the EXACT-PRO user manual definition of “Onset” will not be used for Acute Exacerbation Phase, event duration will not be identified for Acute Exacerbation Phase. Nevertheless, the 4 other parameters will be identified for Acute Exacerbation Phase as below.

On the other hand, the EXACT-PRO user manual definition of “Onset” will be used and event duration will be identified for Stabilisation Phase. Therefore, the 5 parameters will be identified for

Stabilisation Phase as below.

Three-day Rolling Average

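### In the EXACT-based time-to-next-exacerbation analysis, time without a Stabilisation baseline is counted as event-free, which biases the event probability downward by an amount that depends on how the reset rule is read

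*SAP*

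**What the plan says.** SAP 8.1.5 and Appendix C define the Stabilisation Phase baseline as the mean EXACT score over Days 15-21, "with a minimum of 4 days of available data required to compute the baseline value". Otherwise "the baseline EXACT-PRO score for Stabilisation Phase will not be calculated".

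Appendix C makes event detection depend on that value: "Two parameters are required to identify event frequency: (1) Baseline and (2) Onset". One route to onset is a rise of at least 12 points above the patient's "mean Baseline for 2 consecutive days, with Day 1 of the 2 days serving as" the onset day. The other is a rise of at least 9 points above baseline for 3 consecutive days.

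Appendix C also resets the baseline every 28 days in the absence of an event. The first reset uses Days 43-49, again needs 4 diary days, and applies from Week 8 (Day 50). A new event is judged against the last available baseline.

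SAP 8.6.3.13.2 then states: "Patients without a COPD exacerbation or who are discontinued before having it will be considered as" censored. On the analysis set, SAP 8.6.3 says: "The analysis of secondary efficacy endpoints will be performed on the ITT and PP populations". The only data condition for ITT is in SAP 6.1: "Provide a Baseline and at least one post-Baseline FEV1 value". Nothing there concerns the diary.

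**The concern.** A patient without a baseline cannot meet the definition of onset, whatever the diary later shows. The censoring sentence nevertheless places that patient among those with no exacerbation, so the Kaplan-Meier denominator includes person-time in which no event could have been recorded. The estimated probability of a further exacerbation is then too low.

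Gaps in the Day 15-21 diary are foreseeable. Under Appendix C, one missing item voids the day's score and a total of 0 is set to missing. Patients who are unwell or readmitted in Week 3 may also be less likely to complete the diary, though the documents give no data on this.

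The SAP closes comparable gaps elsewhere. The EXACT AUC is set to missing when its baseline is missing (7.1.4.9), and the time-to-discharge analysis limits its set explicitly (8.6.3.14). No such rule appears in 8.6.3.13.2.

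**Working it through.** **The plan's own figure.** The documents give no expected event rate, missing-diary rate or sample size for this analysis. The only stated figure is 85 evaluable patients per arm for FEV1 (SAP 5). It reproduces: difference 100 mL, SD 230 mL, two-sided 0.05 and power 80% give 84 by the normal formula and 84.01, rounded up to 85, by the t-based one. It serves below only as the arm size.

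**Assumed inputs, none from the documents.** True incidence by Week 26 of F = 40% or 60%. Share without a Day 15-21 baseline m = 5% to 25%. Missingness unrelated to relapse risk. Constant hazard, no dropout.

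**Time lost.** Days 15-49 are 35 of the 168 days from Day 15 to Day 182. Appendix C's first event-free period is Weeks 4-7, so patients with a baseline are followed from Day 22: 182 - 22 + 1 = 161 days. Against them, a patient first given a baseline at Day 50 loses Days 22-49, or 28 days, leaving 133.

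**Reading A: no baseline ever, kept at risk to Week 26.** Reported incidence = (1 - m) x F.

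| m | F = 40% | F = 60% |
|---|---|---|
| 5% | 38% | 57% |
| 10% | 36% | 54% |
| 20% | 32% | 48% |

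**Reading B: every such patient gets a first baseline from Days 43-49.** The event probability for a rescued patient is 1 - (1 - F)^(133/161).
- F = 40%: 1 - 0.6^0.826 = 34.4%. Reported: 0.90 x 40 + 0.10 x 34.4 = 39.4% with m = 10%, and 0.80 x 40 + 0.20 x 34.4 = 38.9% with m = 20%.
- F = 60%: 1 - 0.4^0.826 = 53.1%. Reported: 59.3% and 58.6%.

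**Log-rank test with no true difference.** Simulation, 85 per arm, 600 runs per setting, so the simulation standard error at 5% is sqrt(0.05 x 0.95/600) = 0.9 points.

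| Share without baseline, by arm | Reading A, F = 40% | Reading A, F = 60% | Reading B, both F |
|---|---|---|---|
| 10% v 10% | 3.7% | 6.5% | 3.8-4.7% |
| 20% v 20% | 4.8% | 5.0% | 4.3-6.3% |
| 10% v 20% | 8.0% | 14.3% | 4.5-6.3% |
| 5% v 25% | 18.3% | 33.8% | 4.8-6.3% |

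Equal missingness leaves the error rate near 5% under either reading. Unequal missingness raises it only under Reading A.

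**With patients lacking a baseline left out.** Estimates return to about 40% and 60% in both arms, and rejection rates are 3.5-6.8%, consistent with 5% given the simulation error.

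**The case against.** - **No sentence says these patients are kept.** True: it follows from the censoring sentence and the ITT definition. Appendix F, in its example of an EXACT-based exacerbation count, selects patients with a valid response. That text concerns adjusted means from a model, so it does not govern the Kaplan-Meier analysis.
- **The resets restore detection.** A reader might infer that a patient without a Day 15-21 baseline can never have an event detected. The documents do not support that: read literally, Appendix C allows detection from Day 50. Nor do they settle the matter. The reset is for patients with no EXACT event in Weeks 4-7, which cannot be established without a baseline, and its fallback to the previous baseline presupposes that one exists.
- **Reading A is a worst case.** It needs patients who fail every reset window and stay at risk to Week 26. The second condition depends on an unstated censoring date. Table 4 (SAP 7.1.4.10), written for eCRF-recorded exacerbations, censors the row "Subjects who never had COPD exacerbation in study period" at withdrawal or last contact. Table 3 (SAP 7.1.4.8), for EXACT improvement and recovery, censors patients who never reach the event at the last evaluable EXACT assessment. Under Table 3 a patient who stops the diary leaves the risk set early and the bias shrinks.
- **A difference between arms is conjecture.** A reader might infer that the rule favours one arm. The trial is double-blind, dosing ends on Day 5, and no missingness rate is given. Even 36% v 32% is 4 points against a standard error of sqrt((0.36 x 0.64 + 0.32 x 0.68)/85) = 7.3 points, about 0.55 standard errors.
- **The listed endpoint is covered elsewhere.** Time to next moderate/severe exacerbation is analysed from the eCRF form (8.6.3.13.1) and again on adjudicated events (8.8.1), and neither uses an EXACT baseline. This stands and keeps the severity low.

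**Conclusion.** The point holds in a limited form. As written, the EXACT-based analysis counts unassessable time as event-free risk time, and the bias in the event probability is downward. Detection is impossible on Days 15-49 for a patient without the Day 15-21 baseline. After that it depends on whether a reset may supply a first baseline, which the SAP leaves open.

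The size turns on that choice. For an assumed true 40%, the report is about 39-40% if the Week 8 reset rescues everyone. It is 38%, 36% or 32% if 5%, 10% or 20% are never assessable and are kept to Week 26. These rates are illustrations, and missingness is taken as unrelated to relapse risk. An arm difference with no true effect is possible only if missingness differs by arm, and the documents do not show that it does.

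Severity is low. This is a supplementary analysis in a study whose protocol treats all analyses as exploratory (13.5.1).

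**What to change.** Amend SAP 8.6.3.13.2 before unblinding to state that:

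1. Each patient's time at risk starts on the first day a baseline exists.
2. A reset window may supply a first baseline, with delayed entry to the risk set.
3. Patients who never have a baseline are left out.
4. Patients without an event are censored at the last evaluable EXACT assessment, as Table 3 does for those who never reach the event.
5. The number without a baseline is reported by arm. The planned summary of the Stabilisation baseline by regimen (8.6.3.10), which reports n, already supplies most of this.

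The cost is a few sentences and an entry-time variable. The analysis set becomes slightly smaller and is defined by post-randomisation data. If missing diaries are related to relapse risk, some bias remains, so the result should be shown next to the eCRF-based analysis.

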8.6.3.15 Percentage of days with intake of COPD rescue therapy

Based on ‘Rescue Medication’ form of the eCRF, a descriptive summary of the number and proportion of subjects requiring COPD rescue therapy will be provided for each visit per treatment regimen. Moreover, the COPD rescue medication category (Monotherapy: Short-Acting β 2-Agonist [SABA] alone, Short-Acting Muscarinic Antagonist [SAMA] alone, Long-Acting β 2-Agonist [LABA] alone; Dual therapy: SABA+SAMA, SABA+Inhaled Corticosteroids [ICS], LABA+ICS, LABA+SAMA, LABA+SABA; Other) will be presented for each visit per treatment regimen.

Additionally, the percentage of days with intake of COPD rescue therapy (see Section 7.1.4.12 for further details on calculation) will be summarised for each inter-visit period, for the Acute Exacerbation Phase and for the Stabilisation Phase separately, using descriptive statistics by treatment regimen.

8.6.4 Analysis of exploratory endpoint(s)

The analysis of exploratory endpoints will be performed on the ITT and PP populations.

8.6.4.1 Exploratory composite scale endpoints at Weeks 8, 12 and 26

The cumulative proportion of patients presenting each of the criteria below during the study will be summarised per treatment regimen at Days 30, 60, 90, 120, 150 and 180 and compared between treatment regimens at each timepoint using Pearson’s Chi-square test (or Fisher’s exact test as appropriate) (two-sided test at 5% alpha level):

- Worsening of symptoms warranting the addition of another antibiotic or initiation of a new antibiotic
- Worsening of symptoms warranting an increase in dose of oral corticosteroids or initiation of new oral corticosteroids
- Worsening of symptoms requiring additional treatment regimen of oral corticosteroids and/or antibiotics after completion of the initial regimen
- Re-hospitalisation due to worsening of COPD and requiring additional treatment during the duration of the study due to an exacerbation of respiratory symptoms (emergency room admission for longer than 24 hours will qualify as a hospitalisation)
- COPD-related death.

Moreover, the cumulative incidence of CTF (i.e. any one of the individual criteria above is met) will be evaluated at Days 30, 60, 90, 120, 150 and 180 and compared between treatment regimens at each timepoint using Pearson's Chi-square test (or Fisher's exact test as appropriate) (two-sided test at 5% alpha level).

A bar chart will be presented per treatment regimen showing the cumulative incidence of CTF at Days 30, 60, 90, 120, 150 and 180.

In addition, time to CTF will be analysed using the Kaplan-Meier method. Patients who don't meet any one of the individual criteria above or who are discontinued before having it will be considered as "censored" patients.

For the following study periods: [0-4) weeks, [4-8) weeks, [8-12) weeks, [12-16) weeks, [16-20) weeks and [20-26) weeks, the number of clinical treatment failure-free patients at the beginning of the period, the cumulative number of patients with CTF at the end of the period and the probability of having experienced a CTF at the end of the period with the associated two-sided 95% CIs will be presented by treatment regimen. The point estimates and the relative two-sided 95% CIs will be presented by treatment regimen for the 75th, 50th and 25th percentiles. A Kaplan-Meier plot will also be presented. Comparisons between treatment regimens will be performed by means of the log-rank test. The p-values of the pairwise log-rank test comparisons will be displayed on the figure.

8.6.4.2 Change in CRQ from Baseline at Day 14 and Weeks 8, 12 and 26

This exploratory endpoint will be analysed separately during the Acute Exacerbation Phase (from Study Day 1 until Day 14 included) and the Stabilisation Phase (from Day 14 until Week 26).

The CRQ total score and domain scores will be summarised at each visit by treatment group using descriptive statistics. Changes in CRQ from baseline (Visit 1 pre-dose) will be summarised at Day 14 during the Acute Exacerbation Phase by treatment regimen. Changes in CRQ from baseline (Visit 9, Day 14) will also be summarised at each post-baseline visit (Weeks 8, 12 and 26) during the Stabilisation Phase by treatment regimen.

Change in CRQ total score from baseline (Visit 1 pre-dose) to Day 14 (Acute Exacerbation Phase) will be analysed using an ANCOVA model estimating the effect at Day 14, using OC, including treatment, severity of airflow limitation at baseline (pre-dose), blood eosinophils (%) value at baseline (pre-dose), time from start of current COPD exacerbation to first IMP dosing, presence of cardiovascular comorbidities at screening and COPD exacerbation treatment at screening as fixed effects and baseline CRQ total score (Visit 1 pre-dose) as a covariate.

The ANCOVA model results will be presented with LSMEAN and standard error (SE) of each treatment regimen as well as the adjusted mean difference between treatment regimens at Day 14 and associated two-sided 95% CIs. Each pairwise treatment regimen comparison will be tested at an alpha level of 5%. P-values of the effects will also be presented.

A similar ANCOVA analysis as above will be performed for each of the 3 CRQ domain scores during the Acute Exacerbation Phase.

MMRM analysis using an unstructured covariance matrix and the Kenward-Roger adjustment for the denominator degrees of freedom will be performed for statistical comparison of treatment regimens during the Stabilisation Phase with change in CRQ total score as an outcome. Model will consider treatment, severity of airflow limitation at baseline (pre-dose), blood eosinophils (%) value at baseline (pre-dose), time from start of current COPD exacerbation to first IMP dosing, presence of cardiovascular comorbidities at screening and COPD exacerbation treatment at screening as fixed effects and baseline CRQ total score (Visit 9/Day 14) as covariate. In addition the baseline CRQ total score-by-visit and the treatment-by-visit interactions will be included in the model.

LSMEAN and standard error (SE) of each treatment regimen, difference of LSMEANS between treatment regimens and their associated two-sided 95% CIs and corresponding two-sided P-values for Weeks 8, 12 and 26 (Stabilisation Phase) will be estimated by the model. P-values of the effects will also be presented.

The unstructured covariance matrix (which does not presume a particular correlation structure for repeated measurements within patients over time) will be used to adjust for the within-patient error variance covariance. In case model fails to converge, other covariance matrix structures will be considered in the sequence of Ante-dependence, Toeplitz, Heterogeneous AR(1), Heterogeneous Compound Symmetry, and Compound Symmetry.

A similar MMRM analysis as above will be performed for each of the 3 CRQ domain scores during the Stabilisation Phase.

A figure with adjusted mean change from baseline (Visit 9/Day 14) in CRQ total score and domain scores at each visit during the Stabilisation Phase by treatment regimen derived from the linear mixed model will also be provided for each score.

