11.2.5 Exploratory composite endpoints

These endpoints are to be collected in the subject’s eCRF at Day 14, and Weeks 8, 12 and 26.

This evaluates treatment failure as defined by:

1. Worsening of symptoms warranting the addition of antibiotics

2. Worsening of symptoms warranting an increase in dose of oral corticosteroids or initiation of new oral corticosteroids
3. Worsening of symptoms requiring additional treatment of oral corticosteroids and/or antibiotics after completion of the initial regimen
4. Re-hospitalisation due to worsening of COPD and requiring additional treatment during the duration of the study due to exacerbations of respiratory symptoms
5. COPD-related death.

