5 SAMPLE SIZE AND POWER

The sample size is based on a formal statistical calculation using the following assumptions:

1. Endpoint: Absolute change in FEV1 (mL) from baseline to Day 7
2. Minimum clinically significant difference between regimens: absolute change of 100 mL
3. Standard deviation (SD) of the difference = 230 mL (based on a previous study [CBCT197A2201] with BCT197)
4. Superiority design of two BCT197 doses compared to placebo
5. Two-sided alpha (Type 1) error = 0.05
6. No adjustment for multiplicity
7. Beta error (Type 2) = 0.20 (Power = 80%).

Based on the above assumptions, 85 subjects will need to be analysed per dose regimen, resulting in a total of 255 evaluable subjects.

Assuming a dropout rate of approximately 5%, a total of approximately 270 subjects will be randomised to the study.

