- Medication started after Study Day 1 (i.e. \geq Randomisation date + 1) and prior to or on completion of the initial treatment (systemic corticosteroids or antibiotics) for the current COPD exacerbation (started no longer than 24 hours before randomisation).

Criterion 3: Worsening of symptoms requiring additional treatment regimen of oral corticosteroids and/or antibiotics after completion of the initial regimen will be derived from the ‘Prior (Last 6 months medication) and Concomitant Medication’ form of the eCRF. The medications recorded on this form to be considered for this criterion will verify:

- Systemic oral corticosteroids (ATC code ‘H02’ and Route ‘PO = oral’) or Antibiotics (ATC code ‘J01’)
- Medication administered for COPD exacerbations only, i.e. with indication = ‘COPD

exacerbation: current/during the study'

- Medication started after completion of the initial treatment (systemic corticosteroids or antibiotics) for the current COPD exacerbation (started no longer than 24 hours before randomisation).

Criterion 4: Re-hospitalisation due to worsening of COPD and requiring additional treatment during the duration of the study due to an exacerbation of respiratory symptoms will be determined based on the COPD exacerbations experienced after the initial study COPD exacerbation and recorded on the 'Acute Exacerbation COPD' form of the eCRF. This criterion will verify:

- "Has the patient experienced any COPD exacerbations after the initial qualifying study exacerbation subsided?" = 'Yes'
- Treatment: Systemic corticosteroids = 'Yes' or Antibiotics = 'Yes'
- Hospitalisation = 'Yes' or (Emergency room = 'Yes' with a admission longer than 24 hours).

Criterion 5: COPD-related death will be determined based on the COPD exacerbations experienced during the study (including the initial study COPD exacerbation) and recorded on the 'Adverse Event' form of the eCRF. This criterion will verify:

- AE Preferred Term 'Chronic obstructive pulmonary disease'
- Serious AE that 'Results in death'.

The cumulative incidence of CTF as well as each of the individual criteria will be evaluated at Day 30, Day 60, Day 90, Day 120, Day 150 and Day 180.

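### Fixed-day treatment-failure proportions (Days 30 to 180) have no defined denominator and no rule for patients lost event-free, although the same SAP censors those patients in time to failure

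*SAP*

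**What the plan says.** SAP 8.6.4.1 plans two sets of fixed-day comparisons on the ITT and PP populations.

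- For each of the five criteria: "The cumulative proportion of patients presenting each of the criteria below during the study will be summarised per treatment regimen at Days 30, 60", and on to Day 180, tested between regimens by Pearson's chi-square or Fisher's exact test.
- For the composite, the cumulative incidence "will be evaluated at Days 30, 60, 90, 120, 150 and 180 and compared between treatment regimens at each timepoint using" the same tests, with a bar chart by regimen.

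The definition in SAP 7.1.4.13 repeats the six days ("The cumulative incidence of CTF as well as each of the individual criteria will be evaluated at Day 30, Day 60, Day 90" and so on). Neither section gives a denominator or a rule for incomplete follow-up.

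The general rules do not settle it. SAP 8.1.3 allows either the non-missing count or the population count for categorical summaries, and says summary tables are generally on observed cases. SAP 7.2.1 rules out imputation for dropouts, but its reasoning concerns only the primary mixed model. Protocol 9.3.5 treats data after complete withdrawal as missing.

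SAP 8.6.4.1 then adds a second analysis of the composite: "In addition, time to CTF will be analysed using the Kaplan-Meier method". It reports "the probability of having experienced a CTF at the end of the period with the associated two-sided 95% CIs" for periods ending at weeks 4, 8, 12, 16, 20 and 26, with pairwise log-rank tests. Table 6 (SAP 7.1.4.14) censors withdrawn or lost patients at withdrawal or last contact, and censors deaths that are not COPD-related.

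On timing, Protocol 11.2.5 says: "These endpoints are to be collected in the subject’s eCRF at Day 14, and Weeks 8, 12 and 26". Protocol 13.4.3 and SAP 4.3 set the comparison at Weeks 8, 12 and 26. The heading of SAP 8.6.4.1 does too, but its fixed-day tests use the six other days, and SAP 9 does not list the change.

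On loss, SAP 5 says: "Assuming a dropout rate of approximately 5%, a total of approximately 270 subjects will be randomised to the study". SAP 3.1 expects about 255 to complete the study and follow-up.

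**The concern.** A chi-square or Fisher test needs a yes or no for every patient it counts. A patient who withdraws on Day 40 without failing has no known status at Day 180, and the test cannot use the 40 days that were observed. The analyst must either keep the patient as a non-failure or drop the patient, and the SAP does not say which.

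Both choices are biased, in opposite directions, and the bias builds up as follow-up shortens. If loss differs between regimens, the comparison is biased too, and its sign depends on the choice. Because Table 6 censors the same patient, the late CTF risk in the fixed-day table and bar chart need not agree with the Kaplan-Meier risk. The fixed-day p-values would attach to the estimate that cannot use censored time.

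**Working it through.** **The plan's own figures.** With a difference of 100 mL, SD 230 mL, two-sided alpha 0.05 and 80% power, the normal approximation gives 84 per arm. The noncentral t gives 79.99% power at 84 and 80.5% at 85, so the stated 85 reproduces. Per arm, 85/0.95 = 89.5, rounded up to 90, and 3 × 90 = 270. Completion is 255/270 = 94.4%, so loss is 5.6%, consistent with the stated 5%. No CTF rate or power is stated anywhere.

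**Assumptions for the check.** True Day 180 CTF risk p = 20%, 40% or 60%; loss by Day 180 d = 5% (planned), 10% or 20% (assumed); constant and independent hazards; 90 patients per arm.

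**Formulas.** λ = −ln(1−p)/180 and γ = −ln(1−d)/180.

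- True risk by day t: 1 − exp(−λt)
- Full-ITT proportion: E(t) = λ/(λ+γ) × [1 − exp(−(λ+γ)t)]
- Lost event-free patients excluded: E(t)/[E(t) + exp(−(λ+γ)t)]

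Example, p = 40%, d = 5%, t = 180: 180λ = 0.5108, 180γ = 0.0513 and exp(−0.5621) = 0.57. Then E = (0.5108/0.5621) × 0.43 = 39.1%. With exclusion, 0.3908/(0.3908 + 0.57) = 40.7%.

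**Day 180 results.**

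| True risk | Loss | Full ITT | Lost excluded |
|---|---|---|---|
| 20% | 5% | 19.5% | 20.4% |
| 40% | 5% | 39.1% | 40.7% |
| 60% | 5% | 58.7% | 60.7% |
| 20% | 10% | 19.0% | 20.9% |
| 40% | 10% | 38.1% | 41.4% |
| 60% | 10% | 57.4% | 61.5% |
| 20% | 20% | 18.0% | 22.0% |
| 40% | 20% | 36.2% | 43.0% |
| 60% | 20% | 54.7% | 63.1% |

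At 5% loss the Day 180 error is 0.5 to 1.3 points low (full ITT) or 0.4 to 0.7 points high (exclusion). At Day 30 it is at most 0.1 point either way.

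**Comparison of arms at Day 180, full-ITT reading.** Equal loss leaves type I error at 5%. At 5% loss, power for 40% versus 20% falls from 0.839 to 0.828. With equal true risk and unequal loss:

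| Loss, arm A vs arm B (assumed) | Spurious difference | Rejection rate |
|---|---|---|
| 0% vs 10% | 1.0 to 2.6 points | 5.3% to 6.4% |
| 5% vs 15% | 1.0 to 2.7 points | 5.3% to 6.5% |
| 0% vs 20% | 2.0 to 5.3 points | 6.3% to 11.1% |

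The denominator sets the sign. At 40% true risk with 5% versus 20% loss, full ITT favours the arm with more loss by 39.1 − 36.2 = 2.9 points. Exclusion disfavours it by 43.0 − 40.7 = 2.3 points.

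**Visit window.** If Week 26 is taken as Day 182, the ±3-day window lets a completer be seen on Day 179, before Day 180. A yes/no test needs a rule for that patient; a censored estimate does not.

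**The case against.** The strongest defence is that this is a supplementary display of an exploratory endpoint, and a censored analysis of the composite is already planned beside it. Protocol 13.5.1 calls all analyses exploratory. At 45% risk with 90 per arm, the standard error of a difference is √(2 × 0.45 × 0.55/90) = 7.4 points, far larger than the bias at 5% loss. That stands, and it limits the weight of the point. It does not remove the inconsistency, and the five criteria have no censored analysis at all.

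A reader might infer that the SAP counts lost patients as event-free, so that an arm with more withdrawals must look better. This is a likely reading, because criteria are derived from recorded medications and events, but it is not written. SAP 8.1.3 leaves an observed-cases denominator open, and that reverses the direction.

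A reader might also infer from the visit schedule that failure is unascertained once visits stop. SAP 7.1.4.13 derives the criteria from the concomitant-medication, exacerbation and adverse-event forms. Protocol 9.3.5 keeps patients who stop study drug in follow-up for treatment-failure data and asks for telephone contact with those who will not attend. Ascertainment ends only with complete withdrawal or true loss.

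Finally, Kaplan-Meier is not free of fault here. Censoring non-COPD deaths makes one minus Kaplan-Meier overstate cumulative incidence. That is correct and is reflected in the fix.

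**Conclusion.** The point holds as a gap in definition with a better method at hand. The fixed-day CTF proportions lack a denominator and a loss rule. Both available readings are biased increasingly with time, and the SAP's own censoring rule can give a different late figure. No direction of bias can be asserted from the documents.

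At the planned 5% dropout the full-ITT error is about 0.5 to 1.3 points at Day 180; the exclusion error is smaller and of opposite sign. These sizes rest on assumed CTF risks of 20% to 60% and constant, independent hazards. Distortion of the comparison itself requires loss that differs between arms, for which the documents give no figure. This is a low-priority improvement to an exploratory analysis; it does not touch the primary endpoint.

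**What to change.** Take the fixed-day CTF estimates and the bar chart from the time-to-event analysis. Add Days 30, 60, 90, 120, 150 and 180, and the protocol's Weeks 8, 12 and 26, to the time list in the Appendix F code. Report 95% confidence intervals for the pairwise differences in place of the chi-square and Fisher tests.

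Use a cumulative incidence function, with non-COPD death as a competing event for the composite and any death as a competing event for criteria 1 to 4. Amend Table 6 to match. If the crude proportions are kept, state before unblinding the denominator and how patients lost event-free before each day are handled.

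The cost is SAP wording plus a small amount of programming. Kaplan-Meier is planned only for the composite and at week-based period ends. The individual criteria, the six fixed days, the competing-event coding and the intervals for differences are therefore extra runs. Weeks 8, 12 and 26 are already period ends for the composite but not for the criteria. No new data are needed.
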